## 12 EFFICACY ANALYSES

All efficacy analyses will be performed using the Full Analysis Set. Descriptive summaries of all efficacy endpoints will be provided. No hypothesis testing is planned.

### 12.1 Primary Efficacy Endpoint

The primary efficacy endpoint is the change from Baseline to Week 16 in the mFSQ total score.

### 12.2 Secondary Efficacy Endpoints

The secondary efficacy endpoints are the following:

- Change from Baseline to Week 16 on the Schwab and England ADL Scale (Caregiver and Patient version)
- Change from Baseline to Week 16 on the MDS-UPDRS Parts I total score and MDS-UPDRS Part II total score (Caregiver and Patient version)
- Change from Baseline to Week 16 on the CGI-S score for hallucinations and delusions
- Week 16 CGI-I score for hallucinations and delusions
- Week 16 PGI-I score for hallucinations and delusions

### 12.3 Exploratory Efficacy Endpoints

The exploratory efficacy endpoints are the following:

- Change from Baseline to Week 16 on the VRFCAT including adjusted total time T-score, total number of errors T-score, and total number of forced progressions T-score
- Change from baseline to Week 16 on the CSI total score
- Change from Baseline to Week 16 on the NPI-Q Nighttime Behavior Domain Severity and Caregiver Distress scores
- Change from Baseline to Week 16 on the GDS (Short Form)
- Change from Baseline to Week 16 mFSQ score by subscale

- Change from Baseline to Week 16 for each item in MDS-UPDRS Part II

## 12.4 Handling of Missing Data

Scores that are missing, after any imputation of individual missing items as described in Section 5.2, will not be imputed. MMRM analyses will be used as the statistical approach for handling of missing data. Model parameters are simultaneously estimated using restricted maximum likelihood estimation. The MMRM method is unbiased in the estimation of treatment effect under the missing at random assumption and can be thought of as attempting to estimate the treatment effect that could have been observed if all subjects had continued on study for the full study duration.

## 12.5 Multiple Comparisons/Multiplicity

Multiplicity adjustments will not be made as this is an exploratory study and no hypothesis testing is planned.

## 12.6 Examination of Subgroups

Selected subgroup analyses may be performed.

## 12.7 Analysis of Efficacy Endpoints

Descriptive statistics for all exploratory efficacy endpoints listed in [Section 12.3](#) will be tabulated at scheduled timepoints (excluding Screening). In addition, descriptive statistics may be provided for various subscales and individual scale items.

## 12.8 Mixed Model Repeated Measures (MMRM)

The MMRM method with restricted maximum likelihood estimation (REML) will be used for selected efficacy endpoints. The dependent variable will be the change from Baseline. The independent variables in the model will include effects for visit, Baseline score, and Baseline score-by-visit-interaction. An unstructured covariance matrix will be used to model the within patient errors, and the Kenward-Roger approximation will be used to adjust the denominator degrees of freedom.

In the event that the model fails to converge using the unstructured covariance matrix, then only descriptive statistics will be presented.

Summary statistics (observed and change from Baseline, LS means with corresponding two-sided 95% confidence intervals (CIs), and p-values will be presented at each post-Baseline visit for the Full Analysis Set. The primary comparison is based on the LS mean change from Baseline to Week 16.

LS mean  $\pm$  SE from the MMRM model over time for the change from Baseline values will be displayed in line plots for the Full Analysis Set.

The above MMRM model will be used for each of the primary, secondary, and exploratory endpoints. CGI-I score will be analyzed using a similar MMRM model with effects for visit, Baseline CGI-S score, and Baseline CGI-S score-by-visit interaction. PGI-I score will be analyzed using an MMRM model with an effect for visit.

NPI-Q Caregiver and Distress scores will be summarized in shift tables to determine the number and percentage of subjects with Severity scores classified as none, mild, moderate, or severe relative to the same classification at the Baseline visit; and the number and percentage of subjects with Distress scores classified as not distressing at all, minimal, mild, moderate, severe, and extreme or very severe relative to the same classification at the Baseline visit. For the by-visit shift summary, the denominator is the number of subjects with non-missing values at Baseline and the given visit for the given parameter.

For each of the continuous efficacy endpoints (except for CGI-I and PGI-I) the null hypothesis is that the change from baseline to a certain time-point is equal to 0. The corresponding alternative hypothesis is that the change from baseline to a certain endpoint is not equal to 0.

For the CGI-I and PGI-I endpoints the null hypothesis is that the score at a certain time-point is equal to 4 (no change); the corresponding alternative hypothesis is that the score at a certain time-point is not equal to 4.

For each of the continuous efficacy endpoints (except for CGI-I and PGI-I), in addition to MMRM, a paired t-test using a last observation carried forward imputation method will be performed at each post-baseline visit. For CGI-I and PGI-I, a one sample t-test (against a value of 4, indicating no change) will be performed instead of the paired t-test.

Additional exploratory analyses may be conducted on VRFCAT data to adjust for deficits in cognition.

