9.5.1 Primary Analyses

The primary efficacy endpoint, change from baseline to Week 16 in the mFSQ total score, will be evaluated using a mixed-effects model for repeated measures (MMRM). The response variable is the change from Baseline to Weeks 4, 8, 12, and 16 and the fixed effects include visit (Weeks 4, 8, 12, and 16), corresponding Baseline score, and the Baseline score-by-visit interaction. The mFSQ total score will be calculated as the unweighted mean of the subscale scores (Basic ADL, Intermediate ADL, Psychological Function, Social Activity and Quality of Social Interaction). The Work Performance subscale will be excluded, given the age and non-employment status of the intended patient population.

Summary statistics for the mFSQ total score (observed and change from Baseline), least-squares (LS) means and the corresponding 95% CI will be presented.

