### **3.3 Randomization**

This is a single-arm study; therefore, randomization is not applicable.

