### 5.1 General Data Reporting Conventions

For continuous variables, the following summary statistics will be provided: number of subjects, mean, standard error (SE) of the mean, standard deviation (SD), minimum, maximum, and median. Unless specified otherwise, means, medians, and confidence intervals (CIs) will be presented to one more decimal place than the raw data, and the SDs and SEs will be presented to 2 more decimal places than the raw data. In general, the maximum number of decimal places is 4 and values will be truncated to 4 decimal places in situations where there are more than 4 decimal places. Wherever possible data will be decimal aligned.

For categorical variables, summaries will include the number and percentage of subjects in each category; the number of subjects and the percentage of subjects with missing data will be summarized for demographic and baseline characteristics (if applicable). Categories with zero counts will not have zero percentages displayed. Percentages will be presented to 1 decimal place. For demographic (except for Childbearing Potential) and baseline summaries (except for NPI-Q distress), percentages will be calculated by using the total number of subjects as the denominator.

Unless specified otherwise, all statistical tests will be 2-sided hypothesis tests performed at the significance level of 0.05 for main effects. All CIs will be 2-sided, 95% CIs, p-values will generally be presented to 4 decimal places, and p-values less than 0.0001 will be presented as <0.0001

Values that are collected with “<” or “>” signs will generally be analyzed as the numerical value without the sign in tables and figures. In listings, these data will be reported as collected with the sign.

Duration in months will be calculated as (number of days/365.25)\*12 and will be rounded to 1 digit after the decimal point (tenths) for presentation purposes.

Duration in years will be calculated as number of days/365.25 and will be rounded to 1 digit after the decimal point (tenths) for presentation purposes.

Baseline is defined as the last non-missing value prior to the first dose of study drug. All change from baseline endpoints are calculated as the value of the corresponding post-baseline visit minus the value at baseline.

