## **18 CHANGES TO ANALYSES SPECIFIED IN PROTOCOL**

No changes are made to the analyses specified in the protocol.

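### With no control arm, the MMRM standard error for the Week 16 LS mean change treats baseline as fixed, so the primary 95% CI is too narrow and its p-value too small unless change is unrelated to baseline.

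*SAP*

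**What the plan says.** SAP 12.8 fits an MMRM to change from baseline by REML, with unstructured covariance and Kenward-Roger degrees of freedom. On the fixed effects it states: "The independent variables in the model will include effects for visit, Baseline score, and Baseline score-by-visit-interaction". Protocol 9.5.1 has the same model for the mFSQ total score: "the fixed effects include visit (Weeks 4, 8, 12, and 16), corresponding Baseline score, and the Baseline score-by-visit interaction".

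The design is uncontrolled; SAP 3.3 says: "This is a single-arm study; therefore, randomization is not applicable". The headline result is therefore one adjusted mean, not a difference between arms: "The primary comparison is based on the LS mean change from Baseline to Week 16". SAP 12.8 gives it a two-sided 95% CI and a p-value, and sets the hypothesis for the change scores: "the null hypothesis is that the change from baseline to a certain time-point is equal to 0". SAP 5.1 adds that "all statistical tests will be 2-sided hypothesis tests performed at the significance level of 0.05 for main effects".

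SAP 12.8 also plans a second analysis of the change scores: "a paired t-test using a last observation carried forward imputation method will be performed at each post-baseline visit".

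Neither document gives the baseline value at which LS means are evaluated, or says that inference is conditional on the observed baselines.

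**The concern.** Adjusting for baseline is routine in randomised trials, where the quantity of interest is a treatment difference. If the arms share a common baseline slope, sampling variation in the overall baseline mean drops out of that difference. A one-arm mean has nothing for it to cancel against.

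The model treats each subject's baseline as a known constant. The LS mean at the average baseline then gets a variance made of residual scatter only. A new sample of patients would have a different average baseline. If change depends on baseline, the mean change moves with it. The reported standard error leaves that movement out. Kenward-Roger allows for estimated covariance parameters, not for sampling of the covariate mean.

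At stake are the interval and p-value for the primary endpoint, and for every other change score analysed with the same model. CGI-I is affected through its baseline CGI-S covariate. PGI-I, modelled on visit alone, is not affected.

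**Working it through.** **Inputs from the documents.** Single arm (SAP 3.3); fixed effects as above (SAP 12.8, Protocol 9.5.1); two-sided 0.05 level and 95% CIs (SAP 5.1); 89 screened, 53 enrolled, 42 completers (Protocol 3.1). The recruitment figures reproduce: 89 × (1 − 0.40) = 53.4 and 53 × (1 − 0.20) = 42.4. The documents give no standard error, SD or correlation for the mFSQ, so there is no stated precision to reproduce.

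**Assumed inputs.** Baseline-to-Week 16 correlation ρ of 0.3 to 0.9, and ratio r = SD at Week 16 / SD at baseline of 0.8, 1 or 1.25.

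**Formulas** (baseline SD set to 1, complete data):

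- slope of change on baseline = ρr − 1
- residual variance = r²(1 − ρ²)
- reported variance of the LS mean = residual / n
- actual variance over repeated samples = (residual + slope²) / n
- reported SE / actual SE = √[residual / (residual + slope²)]

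**Worked case, ρ = 0.5, r = 1.** Slope = −0.5; residual = 0.75; residual + slope² = 0.75 + 0.25 = 1.00; SE ratio = √0.75 = 0.866. A correct interval is 1/0.866 = 1.155 times as wide. With n = 42 the critical value on 40 df is 2.021. The effective cut-off is 2.021 × 0.866 = 1.750, which gives a two-sided error of 8.8%.

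**SE ratio, with the widening needed for a correct interval:**

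| ρ | r = 0.8 | r = 1 | r = 1.25 |
|---|---|---|---|
| 0.3 | 0.709 (41%) | 0.806 (24%) | 0.886 (13%) |
| 0.5 | 0.756 (32%) | 0.866 (15%) | 0.945 (6%) |
| 0.7 | 0.792 (26%) | 0.922 (8%) | 0.990 (1%) |
| 0.9 | 0.780 (28%) | 0.975 (3%) | 0.975 (3%) |

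**Simulated type I error, n = 42, complete data, 40,000 trials per cell:**

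| ρ | r = 0.8 | r = 1 | r = 1.25 |
|---|---|---|---|
| 0.3 | 16.1% | 11.2% | 8.1% |
| 0.5 | 13.6% | 8.8% | 6.3% |
| 0.7 | 11.8% | 7.0% | 5.0% |
| 0.9 | 12.2% | 5.4% | 5.3% |

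Closed-form values agree to within about 0.3 points. In a zero-slope control (ρ = 0.8, r = 1.25, so ρr − 1 = 0) the error was 5.1%. A paired t-test on the same complete data gave 4.7% to 5.1%.

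**Full MMRM with dropout.** 53 subjects, monotone missing-at-random dropout, mean 41.7 completers, equal SDs, unstructured REML; 3,241 trials at ρ = 0.3 and 3,000 at each other value. A t reference on completers minus 2 df stood in for Kenward-Roger. Monte Carlo SE is 0.4 to 0.5 points.

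| ρ | SAP model | Baseline as a response | SAP model plus variance term | Mean SE / empirical SD, SAP model |
|---|---|---|---|---|
| 0.3 | 10.1% | 4.4% | 4.3% | 0.83 |
| 0.5 | 8.3% | 4.9% | 4.6% | 0.86 |
| 0.7 | 6.5% | 4.8% | 4.5% | 0.92 |
| 0.9 | 5.8% | 5.2% | 4.9% | 0.95 |

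The SAP estimator and the baseline-as-response estimator had the same empirical SDs (0.169, 0.148, 0.113 and 0.066 baseline SDs). The variance term leaves the point estimate unchanged. Neither remedy loses precision.

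**The case against.** **The interval is valid conditional on the observed baselines.** This is true of any covariate-adjusted mean. But neither document states that target. The objective concerns patients with PDP, and the null hypothesis is not worded conditionally. A sentence declaring conditional inference would make the label accurate, but the interval would then answer a narrower question than the objective asks.

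**The size is assumed.** This stands. The largest errors need the spread to shrink by Week 16. Entry limits Schwab & England to 40-80% (Protocol 4.1). If that also narrows baseline mFSQ spread, the omitted term is smaller and the r = 0.8 column less likely. The figures also do not transfer directly to CGI-I, Schwab & England or CGI-S; the last two have baseline ranges truncated by eligibility. The direction does not depend on any of this.

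**Unconditional precision is reported elsewhere.** Raw SDs and SEs of change are planned at each visit, and the paired t-test uses the full variance of change. These help an alert reader. But the raw SE ignores dropout, and the t-test relies on LOCF. Neither is the primary comparison, and neither repairs its interval.

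**The study is exploratory.** Protocol 9.2 and SAP 12 both disclaim hypothesis testing. That limits the consequence. SAP 12.8 nevertheless specifies nulls and p-values, and Protocol 9.5.1 calls for the CI regardless of any test.

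**Conclusion.** The concern holds. For the population mean change at Week 16, the planned standard error is too small whenever change depends on baseline, so the 95% CI under-covers and a true zero change is rejected more than 5% of the time. The exception is a zero slope, meaning ρ × SD at Week 16 equals the baseline SD.

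The direction is certain; the size is not, because the documents supply no mFSQ correlation or SD. With equal SDs, the excess is clear up to ρ = 0.7 (7.0% with complete data, 6.5% in the MMRM with dropout) and small at 0.9 (5.4% and 5.8%). That summary does not extend to unequal SDs: at ρ = 0.9 with r = 0.8 the error is 12.2%, and at ρ = 0.7 with r = 1.25 it is 5.0%.

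The point estimate is not biased by this, and no confirmatory decision rests on the result. The fault is overstated precision in the primary result, repeated across the change-score endpoints. It should be fixed.

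**What to change.** For the change-from-baseline endpoints, adopt one of these in SAP 12.8:

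1. **Baseline as a response.** Model the observed scores at baseline and all scheduled post-baseline visits with visit as the only fixed effect, unstructured covariance, REML and Kenward-Roger. Report Week 16 minus baseline with its 95% CI.
2. **Variance correction.** Keep the current model and evaluate LS means at the mean baseline of the Full Analysis Set. Add slope² × s_B²/n to the LS-mean variance, where slope is the baseline coefficient plus the baseline-by-Week 16 coefficient, s_B² is the sample variance of baseline, and n is the size of that set. Use the matching slope at other visits, and state the degrees of freedom (the check above used completers minus 2).

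For CGI-I, keep the baseline CGI-S covariate with the same correction, or use a visit-only model.

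SAP 18 now says "No changes are made to the analyses specified in the protocol"; it should record this departure from Protocol 9.5.1.

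**Cost.** Wording only; no new data. With equal SDs, intervals widen by about 3% (ρ = 0.9) to 24% (ρ = 0.3). Option 1 estimates 15 covariance parameters for the mFSQ instead of 10 (five occasions instead of four). That slightly raises the risk of triggering the SAP's non-convergence fallback to descriptive statistics only. Option 2 avoids that.

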### **5.2.3 NPI-Q Nighttime Behavior Domain**

The NPI-Q is a self-administered questionnaire completed by informants about patients for whom they care. In this study, the informant is typically the caregiver. There are 12 domains in the full questionnaire; however, only the Nighttime Behavior domain will be completed by informants in this study. Two separate ratings are collected, Severity and Distress, and are scored as follows:

- Severity of the symptom (how it affects the subject): 0=no symptom, 1=mild, 2=moderate, 3=severe
- Distress (how it affects the informant): 0=not distressing at all, 1=minimal, 2=mild, 3=moderate, 4=severe, 5=extreme or very severe

If the informant reports that nighttime behaviors are not present, the Severity score will be set to 0, and the Distress score will remain a missing value. Otherwise, missing Severity and Distress scores will not be imputed.

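### If the unstructured MMRM does not converge, SAP 12.8 falls straight back to descriptive statistics; an ordered covariance fallback would keep the planned missing-data method (minor, mainly for sparse fits)

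*SAP*

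**What the plan says.** SAP 12.8 specifies REML, Kenward-Roger degrees of freedom and a single covariance choice: "An unstructured covariance matrix will be used to model the within patient errors". The scope is wide: "The above MMRM model will be used for each of the primary, secondary, and exploratory endpoints". The rule on failure is: "In the event that the model fails to converge using the unstructured covariance matrix, then only descriptive statistics will be presented". Neither document offers another structure.

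SAP 12.4 leaves missing scores unimputed once the item-level rules have been applied, and states: "MMRM analyses will be used as the statistical approach for handling of missing data". It justifies this under missing at random (MAR).

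Later in 12.8, for continuous endpoints, "in addition to MMRM, a paired t-test using a last observation carried forward imputation method will be performed at each post-baseline visit". CGI-I and PGI-I get one-sample t-tests against 4. The SAP does not say whether any of these tests is still reported when the MMRM fails.

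The number of visits differs by endpoint. For mFSQ, Protocol 9.5.1 says "the fixed effects include visit (Weeks 4, 8, 12, and 16"). VRFCAT has two post-baseline visits (Protocol 9.5.3). The other endpoints are also measured at Week 2 and have five.

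Two further rules matter. SAP 12.3 adds "Change from Baseline to Week 16 for each item in MDS-UPDRS Part II". SAP 5.2.3 says that when the informant reports no nighttime behaviors, "the Severity score will be set to 0, and the Distress score will remain a missing value".

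**The concern.** The plan relies on the MMRM to deal with dropout, which it puts at 20%, and then withdraws the MMRM if one particular covariance matrix cannot be estimated. An unstructured matrix has the most parameters, so it is most likely to fail where data are thin. In that case the Week 16 LS mean and its interval are lost for the endpoint. By-visit summaries then use only subjects still contributing, and are biased if leaving depends on response. Simpler structures would usually still fit and would keep a likelihood-based MAR analysis. The issue is therefore a stated rule that gives a worse result than a routine alternative, not an omission.

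**Working it through.** **1. The plan's own counts.** Protocol 3.1: 89 × (1 − 0.40) = 53.4, stated as 53. 53 × (1 − 0.20) = 42.4, stated as 42. Both reproduce.

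**2. Models under the rule.**
- Primary: 1.
- Secondary: 2 Schwab and England + 4 MDS-UPDRS + CGI-I + CGI-S + PGI-I = 9.
- Exploratory: 3 VRFCAT + CSI + 2 NPI-Q + GDS + 5 mFSQ subscales = 12.
- Subtotal: 1 + 9 + 12 = 22.
- With the 13 Part II items in one or two versions: 22 + 13 = 35, or 22 + 26 = 48.
- Without the 6 mFSQ and 3 VRFCAT models, the five-visit fits number 26 or 39.

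**3. Parameters for T visits.** Unstructured T(T+1)/2; heterogeneous Toeplitz 2T − 1; heterogeneous AR(1) T + 1; compound symmetry 2; fixed effects (visit and baseline-by-visit) 2T.

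| Visits | Unstructured | Het. Toeplitz | Het. AR(1) | CS | Fixed effects |
|---|---|---|---|---|---|
| 2 (VRFCAT) | 3 | 3 | 3 | 2 | 4 |
| 4 (mFSQ) | 10 | 7 | 5 | 2 | 8 |
| 5 (others) | 15 | 9 | 6 | 2 | 10 |

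PGI-I has a visit effect only, so it has 5 fixed effects, not 10.

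**4. How often does the unstructured fit fail?** The documents give no SD, correlation or effect size, so these settings are assumptions: Gaussian data, residual SD 1, AR(1)-type correlation 0.7, monotone dropout. Worse responders leave more often, except in one of the three n = 53, four-visit settings, where dropout is unrelated to response. A non-converged or near-singular REML fit counts as failed.

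| Setting | Missing at last visit | Failed |
|---|---|---|
| 4 visits, n = 53, three dropout settings | 21–26% | 0/60 each, 0/180 in all |
| 4 visits, n = 20 | 43% | 0/40 |
| 5 visits, n = 53 | 24% | 0/25 |
| 5 visits, n = 25 | 23% | 0/25 |
| 5 visits, n = 15 | 25% | 0/25 |
| 5 visits, n = 12 | 28% | 4/25 (16%) |

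Further five-visit runs gave 0/60 at n = 53 (Gaussian), 0/60 at n = 53 with items rounded to 0–4, 0/60 at n = 15, and 0/40 in each of two other settings with 0–4 items. With zero failures, the approximate 95% upper bound is 3 divided by the number of runs: 3/180 = 1.7% for the four-visit model, and 3/(25 + 60) = 3.5% for five-visit Gaussian data at n = 53.

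**5. NPI-Q Distress.** A change score needs the symptom at baseline and at the visit. Assume 50% are symptomatic at baseline and 50–70% of these at each later visit.
- Per visit: 53 × 0.50 × 0.50 = 13.3 to 53 × 0.50 × 0.70 = 18.6, so 13–19 subjects before dropout, for 15 + 10 = 25 parameters.
- Per pair of visits, if presence is independent: 26.5 × 0.50² = 6.6 to 26.5 × 0.70² = 13.0 subjects inform each covariance.

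Simulated with this intermittent pattern, 20% dropout and scores rounded to 0–5, the fit was near-singular in 39/40 runs at 50% presence and 26/40 at 70%. A separate check with 26 subjects and 60% presence gave 8/8. Near-singularity is a proxy for a convergence failure in SAS, not the same thing.

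**6. Cost when the rule is used.** Bias at Week 16 in SD units, four visits, n = 53, true change 0.40, Monte Carlo SE about 0.02:

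| Dropout | MMRM | Observed-case mean | LOCF |
|---|---|---|---|
| Unrelated to response | +0.032 | +0.030 | −0.011 |
| Depends on response | +0.048 | +0.166 | −0.095 |
| Depends more strongly | +0.007 | +0.188 | −0.193 |

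**7. Optional looks.** SAP 15 allows an efficacy analysis at 50%: 53 × 0.50 = 26.5 subjects, of whom 26.5 × 0.80 = 21 would be completers. SAP 12.6 allows subgroups. Neither section says whether the convergence rule applies.

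**The case against.** The study is single-arm and exploratory, has no formal sample size, and both documents describe its efficacy reporting as descriptive without planned hypothesis testing. A fallback to descriptive statistics fits that stance, and because it is written in advance nobody can choose a covariance structure after seeing the data. The summaries still give n, mean, SD and SE (SAP 5.1), so an interval for the observed mean can be recovered. If dropout is unrelated to response, little is lost. All of this stands and limits the severity. It does not make the rule the better choice, since an ordered list is equally pre-specified.

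The clearest exposed endpoint is also a poor advertisement for the remedy. Distress is blank because the symptom is absent, not because the subject left. An MAR model would impute a notional distress level to symptom-free visits, which is not the quantity SAP 12.4 describes. A simpler covariance may converge without resolving that. SAP 12.8 already plans shift tables for Distress with defined denominators. This stands too.

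A reader might infer that after a failure the LOCF t-test becomes the only inference. The documents do not settle this. The failure rule says that only descriptive statistics are presented, while the t-tests are planned without condition. The defect is the ambiguity.

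**Conclusion.** The point holds as a minor, cheap improvement. On failure, the rule removes the MAR-based method that SAP 12.4 names and leaves observed-case means, with t-tests of unclear status. The loss could reach 0.17–0.19 SD on a change of 0.40 SD if dropout depends on response, and is negligible if it does not.

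A reader might infer from the scope that the primary result, or the 26–39 five-visit models in general, is likely to lose its model. The documents do not support that. A count of models is not a failure rate, and at the planned 53 enrolled and 42 completers no failures appeared for the four-visit model, for five-visit Gaussian data or for simulated 0–4 items. Very skewed items with almost no variance were not tested. Plausible exposure is chiefly NPI-Q Distress, and possibly small subgroups or the 50% look. The Distress figures rest on an assumed symptom rate, and all failure and bias figures on the assumed correlation and dropout pattern.

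**What to change.** Replace the failure sentence in SAP 12.8 with a paragraph that does the following:

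- Fits unstructured, then heterogeneous Toeplitz, then heterogeneous AR(1), then compound symmetry; uses the first that converges; and goes to descriptive statistics only if all fail.
- Names the inference method for the simpler structures: either Kenward-Roger with model-based SEs, or a small-sample-corrected sandwich SE with stated degrees of freedom. An uncorrected sandwich SE tends to be too small in the sparse data where the fallback would be used.
- Reports the structure used in each table.
- States whether the LOCF paired t-tests and the one-sample t-tests are still reported after non-convergence.
- Says whether the rule applies to subgroup runs and the 50% efficacy look.
- For NPI-Q Distress, rests the reporting on the planned shift tables.

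The cost is one SAP paragraph and a few lines of code. The downside is that a simpler structure may be misspecified, which can bias the LS mean somewhat under MAR; a sandwich SE does not repair that. Reporting the structure lets readers see where this applies.
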